All patients with myocarditis (or any alternative final diagnosis), will undergo standard cardiological optimal medical treatment (COMT), as indicated. By converse, aetiology-dependent treatment will be performed only in patients with a final diagnosis of any *active* (acute, fulminant, chronic active) myocarditis of defined aetiology (EMB-proved). Multidisciplinary assessment, including infective disease specialists (in viral/infective myocarditis), immunologists (in non-infective/autoimmune myocarditis) or any other specialist as needed, will be used to identify indications to treatment, drug choice (either approved or with a justified off-lable indication), treatment duration and safety profile, aiming at the best patients' interest. Toxic myocarditis will be treated accordingly, by evaluating the opportunity of withdrawing pathogenic noxa.

This protocol will not interfere with local best clinical practice.

Patients with *non-active* myocarditis (previous or healed) or with non-myocarditis, will undergo "standard FU" (see below). Patients with *active* myocarditis will undergo "intensive FU" (see below).

Independently of FU modalities, diagnostic reassessment will be considered in the presence of at least one of the following *instability* criteria: a) new unexplained cardiac symptoms (dypnoea, chest pain, syncope, palpitation); b) new unexplained increase in troponin or natriuretic peptides; c) new imaging abnormal signs; d) new unexplained clinically relevant arrhythmias. Diagnostic reassessment will include second-level imaging and/or EMB, as shown above. Subsequent therapeutical workup will be in line with the above explanations. In stable patients or undergone myocarditis healing, exercise stress test will be obtained, whenever possible.

Panel B - Diagnostic and therapeutical workup of patients with arrhythmias

In parallel with (and independently of) Panel A content, patients with arrhythmias (group A) will undergo specific diagnostic and therapeutical management for arrhythmias, as a result of the integration between international guidelines recommendations and the experience of a third-level center international referral center (San Raffaele Hospital, Milan) for arrhythmia management and ablation.

To oversimplify, 4 groups of patients will be considered.

1. Group 1: major ventricular arrhythmias (haemodynamically unstable VT, hu-VT; ventricular fibrillation, VF).

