 F. Different myocarditis stages and differential diagnoses G. Isolated vs. in the context o a systemic disease or genetic disease H. Myocarditis vs. perimyocardis/ myopericarditis 	 Validation of biomarkers and imaging techniques in monitoring response to treatment (group E) Identification of optimal follow-up timeline Other analyses
-------------------------------------------------------------------------------------------------------------------------------------------------------------------------------------------------------------------------------------------------------	-------------------------------------------------------------------------------------------------------------------------------------------------------------------------------------------------

FOLLOW-UP VARIABLES

Any quantitative and qualitative parameters detectable by medical history, objetcive examination, biomarkers, 12-leads ECG, signal averaged ECG, continuous telemonitoring (during nwe hospitalization or in device carriers), Holter ECG (at least 24-hours, possibly 12-leads), color Doppler transthoracic echocardiogram, coronary angiography or CT scan, stress tests, CMR, DECT, PET scan (alone or in association/fusion), genetic tests, tilting test, electrophysiological study (either invasive or nonivasive), electroanatomical map, any other imaging or laboratory exam identified as clinically-relevant.

FOLLOW-UP TIMELINE

A clinical time zero (t0) will be considered as the start point for FU. t0 indicates the timing of myocarditis diagnosis, as assessed by EMB (first choice) or by imaging techniques (secondo choice).

FU calendar will be variable based on clinical indications. As a general line, intensive FU will be planned for the first two years (month 3, month 6, month 9, month 12, month 18, month 24). For patients needing a strict control for relevant clinical issues, minimal FU reassessment is set at 2 weeks timespan. In the absence of clinical issues, from month 24 FU will be performed every 6-12 months up to the end of the study.

FOLLOW-UP EXAMS

- Standard FU: cardiological (or multidiciplinary) assessment 1-2/y with blood exams (at least troponin, natriuretic peptides, and inflammatory indexes), 12-leads ECG, Holter ECG monitoring, device interrogation (in device carriers), and color Doppler transthoracic echocardiogram. Second-level imaging techniques (CMR, DECT, PET scan) or other exams will be performed based on clinical indications.

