- Intensive FU: cardiological (or multidiciplinary) assessment 1-2/y with blood exams (at least troponin, natriuretic peptides, and inflammatory indexes), 12-leads ECG, Holter

ECG monitoring, device interrogation (in device carriers), and color Doppler transthoracic echocardiogram. Minimal reassessment timespan is 2 weeks. At least one second-level imaging techniques (CMR, DECT, PET scan) will be performed by 12 months (approximately at 3, 6, 9, or 12 months based on clinical indications). Exercise stress test will be performed whenever clinically indicated, usually not before proved myocarditis healing. Other exams will be performed based on clinical indications.

STUDY DURATION

Estimated study duration is 23 years (from Jaunary 2013 to December 2035). In detail:

- Retrospective enrollment: from January 2013 to local institute review board approval.
- Prospective enrollment: from local institute review board approval to Dicember 2025 (estimated enrollment end).
- FU duration per patient: 10 years.
- Estimated last FU for last enrolled patient: December 2035.

CONFOUNDING FACTORS

Not applicable.

EPIDEMIOLOGIC DATA

Because of multiple clinical presentations and heterogeneous diagnostic techniques, myocarditis incidence is widely variable [1].

At our institution, the mean rate of clinically suspected myocarditis is not inferior to 4 new cases/month. Epidemiology may be different at other centers.

Target numbers reported in Table 1 are reasonable.

DATA COLLECTION AND STATISTICAL ANALYSIS

Two enrollment modalities are accepted for this study: 1) prospective enrollment: at myocarditis diagnosis (following local institute review board approval); 2) retrospective enrollment: during FU of myocarditis patients (diagnosed before local institute review board approval).

Considering incidence rate, local and general epidemiology, enrollment of 1000 myocarditis cases by December 20205 is expected, including retrospective and prospective enrollment. For aim 1, 95% confidence intervals of 81-89% and of 75-85% are estimated for EMB and CMR, with 85% and 80% sensitivity, respectively. These data are consistent with updated knowledge. EMB will be considered as the diagnostic gold standard, as indicated [1].

Both baseline and FU data will be collected for each enrolled patient. CRF form reports the main study variables, in the form of an Excel document.

Statistical analyses will be performed by certified programs (i.e. SPSS).

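### The protocol calls confounding not applicable, although Aims 5E and 4 compare treated with untreated patients selected by disease activity and biopsy; separately, the intensive follow-up rate contradicts its calendar

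*Protocol*

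**What the plan says.** **Confounding.** The whole text of the protocol's Confounding Factors section is "Not applicable". Elsewhere the protocol plans two comparisons by treatment:

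- Aim 5E (Aims; Table 1, row 5) sets aetiology-driven therapy against standard cardiological treatment. The primary variable of that row is the difference in major outcomes.
- Aim 4 (Table 1, row 4) lists, among its secondary variables, healing times in treated against untreated patients.

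Ethical Issues says that nothing is randomised and that groups form from clinical features and individual workup. Study Design, Panel A, states the treatment rule: "aetiology-dependent treatment will be performed only in patients with a final diagnosis of any" active myocarditis with a defined, EMB-proved aetiology. Panel A also says who gets an EMB. Unstable patients go directly to it. Stable patients have second-level imaging first, and EMB only if clinically indicated.

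**Visit rate.** Follow-up Timeline: "intensive FU will be planned for the first two years (month 3, month 6, month 9, month 12, month 18, month 24". Follow-up Exams gives the rate for the same schedule as "Intensive FU: cardiological (or multidiciplinary) assessment 1-2/y with blood exams". The standard schedule has the identical rate: "Standard FU: cardiological (or multidiciplinary) assessment 1-2/y with blood exams".

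**Scans.** For intensive follow-up, "At least one second-level imaging techniques (CMR, DECT, PET scan) will be performed by 12 months", timed "approximately at 3, 6, 9, or 12 months based on clinical indications". For standard follow-up, "Second-level imaging techniques (CMR, DECT, PET scan) or other exams will be performed based on clinical indications".

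**The concern.** In an unrandomised study, a factor that drives both treatment and outcome distorts the crude comparison between treated and untreated patients. Here the protocol's own algorithm creates such factors: disease activity, clinical stability, and whether a biopsy was taken and gave an aetiology. To declare confounding inapplicable is therefore a wrong statement, not a detail left for later. An analysis plan that adjusted properly would have to contradict this section.

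The stake is highest for Aim 5E, where the comparison concerns the major endpoints, including death, malignant ventricular arrhythmia and transplantation. A crude result could credit the treatment with harm or benefit that belongs to the patients selected for it.

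The visit-rate conflict is a different and smaller matter: centres are given two schedules for the same patients in year 1.

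**Working it through.** **1. Who can be treated, read from Panel A.**

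| Patient | Route to EMB | Eligible for aetiology-dependent treatment |
|---|---|---|
| Unstable | EMB directly | Yes, if active with a defined, EMB-proved aetiology |
| Stable | Imaging first, EMB only if indicated | Same condition, so only if an EMB was done |
| Active, no EMB | None | No |
| Non-active (previous or healed) or not myocarditis | Any | No |

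Two consequences follow.

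- *Selection into eligibility.* The treated group comes only from the first two rows. An untreated group defined simply as everyone else mixes all four. Stage and EMB status then differ by rule, and stability can differ because it governs access to EMB. For patients in the last two rows the rule sets the chance of treatment at zero. Adjustment cannot supply treated counterparts for them, so restriction is needed. Restricting to active disease alone would not be enough, because active patients without EMB would still be in the untreated group.
- *Selection within eligibility.* Among eligible patients, specialists decide on indication, drug and duration, and patients may refuse. Those decisions follow presentation, severity and aetiology, so adjustment is needed as well as restriction.

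**2. Illustration of size (inputs assumed, none from the protocol).** Suppose treatment has no effect and a single factor, instability, lowers recovery by month 12. Then

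false difference = (unstable share, treated − unstable share, untreated) × (recovery, stable − recovery, unstable).

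Assume an unstable share of 0.2 in the untreated group and recovery of 0.75 in stable patients. Aim 4's target is 500; a 250/250 split is assumed.

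| Unstable share, treated | Recovery, unstable | Treated recover | Untreated recover | False difference | Studies with p<0.05 |
|---|---|---|---|---|---|
| 0.3 | 0.65 | 0.75 − 0.3×0.10 = 72% | 0.75 − 0.2×0.10 = 73% | 1 point | 5.7% |
| 0.5 | 0.55 | 0.75 − 0.5×0.20 = 65% | 0.75 − 0.2×0.20 = 71% | 6 points | 30% |
| 0.6 | 0.45 | 0.75 − 0.6×0.30 = 57% | 0.75 − 0.2×0.30 = 69% | 12 points | 80% |

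The last column uses the normal approximation. In the middle row the standard error is √[(0.65×0.35 + 0.71×0.29)/250] = 0.0416, so z = 0.06/0.0416 = 1.44 and the chance of p<0.05 is Φ(1.44 − 1.96) ≈ 30%. Within each stability stratum the difference is zero, so stratifying on this factor would remove the bias.

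**3. Visit rate (from the protocol alone).** The stated rate of 1–2 a year is not reproduced by the calendar.

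| Period | Calendar | Rate line |
|---|---|---|
| Year 1 (months 3, 6, 9, 12) | 4 | 1–2 |
| Year 2 (months 18, 24) | 2 | 1–2 |
| Months 0–24 | 6 | 2–4 |

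The conflict is confined to year 1.

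**The case against.** The strongest reply has three parts.

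*Adjustment is already foreseen.* Data Collection and Statistical Analysis mentions multivariable regression and promises suitable tests for each aim, and a covariate list commonly belongs in an analysis plan. So a reader should not infer that the protocol rules out adjustment altogether. But that sentence concerns risk stratification and survival analyses and names no confounder, and it does not undo an explicit statement that confounding does not apply.

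*The algorithm is loose.* Study Design calls the panels approximate and allows exceptions, so a few patients outside the rule may be treated. This softens the zero chance of treatment but does not make the groups comparable.

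*The calendar is flexible.* Follow-up Timeline calls it variable and a general guide, and reassessment may be as frequent as every two weeks. This makes the rate line look like a copying slip. It does not explain why the intensive rate equals the standard one.

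A stronger reading is also tempting: that clinically timed scans, with only one assured by month 12, make the healing-time comparison wrong as planned. The documents do not support it. Nowhere does the protocol say that recovery will be dated at the scan or analysed in a particular model. One scan is a minimum, and Panel A adds reassessment by imaging and/or EMB when instability criteria are met. Patients assigned to standard follow-up under Panel A have previous or healed disease or no myocarditis, so the lack of an assured scan for them says little about healing. Nor does the visit-rate slip reach the healing data, because the scan commitment is a separate sentence that already uses months 3, 6, 9 and 12.

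**Conclusion.** The point holds on the text. Confounding does apply to Aim 5E and to the treated-against-untreated comparison in Aim 4, because the treatment and biopsy rules in Panel A tie treatment to activity, stability and EMB-proved aetiology. It deserves correction, more for Aim 5E than for Aim 4, where the comparison is one of several secondary variables.

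The size and direction of any bias cannot be derived from the documents. The 1 to 12 points above show only what assumed imbalances would produce, and they should not be read as an estimate for this study.

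The visit rate is a separate, minor contradiction: four visits against one to two in year 1, with agreement in year 2. It rests on no assumption.

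How healing time is handled between scans is a matter for the analysis plan and is not an error in the protocol.

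**What to change.** 1. **Confounding Factors.** Replace the present entry with the measured drivers of treatment: clinical presentation and stability, disease stage, aetiology, severity and centre. State that the treatment comparisons in Aims 5E and 4 are adjusted for them.
2. **Comparison set.** Restrict the main treated-against-untreated comparison to patients who meet Panel A's eligibility rule, meaning active disease with a defined, EMB-proved aetiology. Report active patients without EMB separately.
3. **Intensive follow-up rate.** Restate it as four visits in year 1 and two in year 2, more if clinically needed.
4. **Optional, for the analysis plan.** Treat healing time as interval-censored between the last scan without recovery (or t0) and the first scan with recovery, using recorded scan dates.

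Items 1 to 3 are text changes that add no scans and leave local practice alone. The price is a smaller comparison set and wider confidence intervals. Unmeasured reasons for treating or not treating will remain, and the report should say so. Item 4 may need software beyond basic routines.

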 - C. Non-arrhythmic myocarditis subrgoups (i.e.: fulminant, acute coronary syndrome-like, pericarditis-like, heart failure, nonischaemic dilated /hypokynetic cardiomyopathies of unknown aetiology...).
 - D. Infectious vs. aoutoimmune vs. toxic myocarditis.
 - E. Myocarditis treated by aetiology-based treatment vs. isolated cardiac medical treatment.
 - F. Myocarditis at different disease stages: acute, hyperacute, fulminant, chronic active, post-inflammatory, or active vs. previous vs. non-myocarditis.
 - G. Myocarditis presenting as organ-specific diseases vs. in the context of a genetic disorder or systemic disease.
 - H. Myocardits vs. peri-myocarditis/myo-pericarditis.
 - I. Other analyses.

STUDY DESIGN

Our study, previously designed as a single-center experience, is multicenter, observational and both retrospective and prospective.

Retrospective phase includes all clinical data occurring before the index event (hospitalization or clinically suspected myocarditis) and myocarditis diagnosis. Prospective phase includes all data following index event and myocarditis diagnosis.

Any adult patient with clinically suspected myocarditis, of any clinical presentation and any degree of severity, will be considered as suitable for study enrollment.

Patients will undergo diagnostic and therapeutical strategies considered as clinically indicated in a patient-tailored manner, as suggested by international guidelines recommendations and best local clinical practice. Patients will be free of either accepting or refusing any diagnostic or therapeutical proposal. Whenever accepted, data will be simply collected and analyzed.

Based on clinical presentation, patients will be divided into two groups, arrhthmic (group A) and non-arrhythmic (group NA, including any other clinical presentation).

Independently of A/NA groups, all patients will undergo optimal diagnostic and therapeutic strategies, as summarized in panel A. In parallel, special diagnostic and therapeutical strategies will be performed in patients with arrhythmic presentation or evidence of arrhythmias, as shown in panel B. Proposed flowcharts (panels A and B) represent only an approximate algorithm. Exceptions can be made in single cases, based on clinical indications.

Panel A – Diagnostic and therapeutical workup in all patients.

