- Age \geq 18 years.

- Clinically suspected myocarditis [1].
- Enrollment performed by one of the participating Centers.

EXCLUSION CRITERIA

- Absence of written informed consent.
- Age < 18 years (paediatric population).

VARIABLES AND ENDPOINTS

The main study variables are reported in Table 1 and in CRF. Endpoints will include:

- Major endpoints: death; cardiac death; malignant ventricular arrhythmias (= VT, VF, appropriate ICD therapy); heart transplantation; end-stage heart failure.
- Minor endpoints: minor arrhythmias (NSVT; supraventricular arrhythmias; bradyarrhythmias); structural or functional myocardial abnormalities (any chamber dilation, systolic or diastolic dysfunction, including strain analysis, pericardial, vascular or valvular involvement, any other detectable abnormalities); abnormalities detectable by advanced imaging techniques (Lake Louise criteria and T-mapping techniques at CMR; any qualitative or quantitative imaging abnormality detectable by CMR, DECT or PET scan, or other imaging techniques, alone or in association); clinical variables (signs and symptoms related to cardiac or multisystemic disease; identification of associated diseases); blood exams abnormalities (inflammatory indexes; cardiac injury, inflammation or stress biomarkers; cardiac and extracardiac autoantibodies; genetic tests; tissue/organ damage indexes; markers of treatment toxicity; others); anatomical or functional abnormalities of coronary macro or microvascular structures (coronary angiography; CT scan; histology; provocative stress tests, nuclear medicine techniques); necessity of invasive elctrophysiological techniques (electrophysiological study; arrhythmia ablation; device implant) and related findings; indications and timing for primary and secondary prevention device implant, in relation with different therapeutic strategies; myocarditis recurrences; response to general and specific treatement; multiparametric modeling of prognostic risk stratification and response to treatment prediction; elaboration of multidisciplinary workup models.

The main pimary and secondary variables are reported in detail in Table 1.

Tabella 1

N	Aim	N patients	Primary Variables	Secondary variables

MYOCAR - Version V03 - Multicenter

Principal Investigators: [name] - [name]

1 Comparison between EMB 1000 Diagnostic Inflammation 	ory activity (presence; type;
and second level imaging concordance quantificat	
findings • Fibrosis (p	resence; type; quantification)

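### The eligibility sections admit patients on clinical suspicion but the enrolment rule takes them at a myocarditis diagnosis, so patients in whom myocarditis is excluded have no stated entry route or time zero

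*Protocol*

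**What the plan says.** Eligibility rests on suspicion. Study Design states: "Any adult patient with clinically suspected myocarditis, of any clinical presentation and any degree of severity, will be considered as suitable for study enrollment". Study Population repeats this, and the Inclusion Criteria ask for clinical suspicion, not for a confirmed diagnosis.

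Several places plan for patients who turn out not to have the disease. Aim 5F compares "active vs. previous vs. non-myocarditis", and Table 1 lists the same item as disease stages together with differential diagnoses. Panel A assigns standard follow-up to patients without myocarditis and refers to the treatment of patients with another final diagnosis. Among the secondary variables of aim 1, Table 1 includes the comparative accuracy of biopsy, CMR/DECT and PET, and differential diagnosis from other cardiac diseases.

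Data Collection and Statistical Analysis is narrower. It opens with "Two enrollment modalities are accepted for this study" and names them: "prospective enrollment: at myocarditis diagnosis (following local institute review board approval", and "retrospective enrollment: during FU of myocarditis patients (diagnosed before local institute review board approval". The target there is "enrollment of 1000 myocarditis cases". Follow-up Timeline sets t0 at the myocarditis diagnosis, made by biopsy or, as second choice, by imaging. The only accrual figure, in Epidemiologic Data, counts suspected cases: at least 4 a month at the head centre. The Exclusion Criteria list "Absence of written informed consent", and no exception is stated.

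**The concern.** A study that enrols on suspicion and a study that enrols on diagnosis have different denominators. The protocol describes both. If a centre follows the enrolment paragraph to the letter, the patients left out are those whom 5F and the accuracy and differential-diagnosis items of aim 1 need for comparison. If another centre follows the inclusion criteria, the pooled database mixes two case definitions, and the number of comparators depends on the centre. A later analysis plan cannot restore patients who were never entered.

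A second, smaller consequence concerns mortality. Death is a major endpoint, and Panel A foresees life-threatening presentations in which support comes before the work-up is complete. A patient who dies in that interval has no diagnosis, and so neither an entry route nor a t0.

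**Working it through.** **Step 1. The passages side by side.**

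| Patient (consenting adult, clinically suspected) | Meets inclusion criteria | Route under the enrolment paragraph | t0 defined | Used in |
|---|---|---|---|---|
| Diagnosed after local board approval | yes | prospective | yes | all aims |
| Diagnosed before approval, in follow-up | yes | retrospective | yes | all aims |
| Myocarditis excluded | yes | none | no | 5F; Panel A standard follow-up; aim 1 accuracy and differential diagnosis |
| Dies before diagnosis | yes | none | no | death as major endpoint |
| Dies after prospective enrolment | yes | prospective | yes | kept |

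The third row is the contradiction. It needs no arithmetic.

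**Step 2. What the plan's own figures say about the unit.** The target is 1000 myocarditis cases, while the rate is at least 4 suspected cases a month. January 2013 to December 2025 is 13 × 12 = 156 months, so the head centre sees at least 4 × 156 = 624 suspected patients. The confirmed share is not in the protocol. Assuming 50-80%, that is 624 × 0.5 = 312 to 624 × 0.8 = 499 confirmed cases.

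The stated precision for aim 1 does not settle the unit either. With n = 1.96² p(1−p)/h², the interval 81-89% around 85% implies 1.96² × 0.85 × 0.15 / 0.04² ≈ 306. The interval 75-85% around 80% implies 1.96² × 0.80 × 0.20 / 0.05² ≈ 246. At n = 1000 the intervals would be 82.8-87.2% and 77.5-82.5%. That mismatch is a separate matter. What matters here is that the precision statement covers sensitivity only.

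**Step 3. Effect on aim 1.** The protocol takes biopsy as the reference standard. Let a = both tests positive, b = biopsy positive and imaging negative, c = biopsy negative and imaging positive, d = both negative.

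- Sensitivity of imaging = a/(a+b). Both cells can enter under the literal rule.
- Specificity of imaging = d/(c+d). Cell c can enter, because imaging may establish the diagnosis. Cell d cannot.
- With one imaging technique, the computed specificity would be 0/(c+0) = 0, whatever its true value.
- With several techniques, a patient negative on biopsy and CMR might enter through DECT or PET. Cell d is then not wholly empty, but it is filled only by patients positive on another test, so the estimate remains biased.

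**Step 4. Size.** Under the literal rule the number of non-myocarditis comparators is 0. If 1000 suspected patients are enrolled, the number is 1000 × (1 − confirmed share). The 95% half-width for an assumed specificity of 80% is 1.96 × √(0.80 × 0.20 / n).

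| Confirmed share (assumed) | Comparators n among 1000 suspected | Half-width, points | Suspected patients needed for 1000 confirmed |
|---|---|---|---|
| 50% | 500 | 3.5 | 2000 |
| 70% | 300 | 4.5 | 1429 |
| 80% | 200 | 5.5 | 1250 |
| 90% | 100 | 7.8 | 1112 |

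The half-widths are a best case, since they suppose that every comparator has both tests. In stable patients biopsy is done only when clinically indicated.

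**The case against.** The strongest reply is that nothing gives the enrolment paragraph priority. Eligibility is set out consistently in Study Design, Study Population and Inclusion Criteria. The two modalities can be read as saying only whether a patient counts as prospective or retrospective, according to the date of local approval. Panel A shows that the authors mean to follow patients without myocarditis. A reader might infer that the protocol as a whole drops the comparators, and the documents do not support that. What stands against the reply is that both modalities are tied to a diagnosis, no third is offered, and t0 is tied to the same diagnosis. The timing-only reading is possible, but it does not give these patients an entry route or a starting date.

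On aim 1, the primary variable is diagnostic concordance, the planned precision concerns sensitivity, and comparative accuracy is a secondary item. Patients positive on imaging but negative on biopsy can still enter, so discordance can be observed. All of this is right. The harm falls on specificity and on the double-negative patients, not on sensitivity.

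A reader might also infer that early deaths in general are lost. They are not: deaths after prospective enrolment are kept. Nor would moving entry to suspicion recover every death before diagnosis, because written consent is required under either rule.

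Finally, 624 against 1000 might be read as a shortfall. It is not one. The rate is a floor for a single centre, the target is multicentre, and the protocol notes that epidemiology may differ elsewhere.

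**Conclusion.** The point holds as an internal contradiction about who enters the study. Applied literally, the enrolment paragraph and the t0 definition leave patients in whom myocarditis is excluded without a route in or a time zero. The 5F non-myocarditis group would then be empty, and specificity in aim 1 could not be estimated without bias. Applied unevenly, the paragraph would make case mix depend on the centre. Patients who die before diagnosis would also be missed.

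This conclusion rests on the text alone. The counts of 100 to 500 comparators per 1000 suspected patients rest on an assumed confirmed share of 50-90%, and the half-widths on an assumed specificity of 80%. Neither figure is in the protocol, and the contradiction does not depend on them. The unit of the 1000 target is unclear, but its feasibility is not called into question. The wording should be corrected. The plan's other analyses of confirmed cases are unaffected.

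**What to change.** - In Data Collection and Statistical Analysis, set prospective entry at clinical suspicion (the index event, a term Study Design already uses). Let retrospective entry cover patients evaluated for clinically suspected myocarditis before local approval. State that patients with another final diagnosis stay in the database.
- In Follow-up Timeline, extend t0 to patients without a myocarditis diagnosis. One option is to record the index event date for everyone and use it as the common origin in comparisons that include them, with the diagnosis date kept as a second date.
- State whether 1000 counts suspected or confirmed cases, and give the accrual rate in the same unit.
- Because written consent is mandatory, say that patients who die before consent are not captured, and report this as a limit on conclusions about early mortality.

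The cost is a few sentences, plus consent and baseline data entry for some additional patients whom the inclusion criteria already admit. If 1000 is meant as confirmed cases, the number entered will be larger, as Step 4 shows.
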